The primary outcome measure will be a change in the total score on the Neuropsychiatric Inventory Questionnaire (NPI-Q) over 12-weeks. We expect the group receiving Feru-guard will have a greater improvement in total NPI score compared to the placebo group at 12-weeks.

Secondary Aim 2.) Measure the effect Feru-guard supplementation has on caregiver burden and quality of life, and global cognition in participants. We will collect data on the effect of Feru-guard supplementation on caregiver burden (NPI-Q subscale of caregiver distress), the Zarit Burden Interview (ZBI) screening

version, and caregiver quality of life (SF-12) over 12 weeks. We will also collect data on changes in global cognition of participants over 12 weeks using the Montreal Cognitive Assessment (MoCA). We will compare secondary outcomes between Feru-guard and control group.

The data generated in this pilot study will be used to aid in the design of a larger clinical trial that can more definitively assess the effects of Feru-guard for BPSD in dementia.

B. BACKGROUND:

B.1. Behavioral and Psychological Symptoms of Dementia (BPSD)

[figure not shown]

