A total of 70 participants 55 years and older will be enrolled, this accounts for a 10% drop out rate. To achieve an enrollment of 70 participants, accounting for a 25% screen fail rate, we anticipate needing to screen 95 participants. Due to the study population being demented, each participant must have a committed caregiver who is able to act as their study partner. The study partner will be asked to accompany the participant to each onsite visit and complete some questionnaires pertaining to the participant's health.

D.2.2. Inclusion and Exclusion Criteria Inclusion

- 55 years old or older.
- Diagnosis of AD, vascular, and mixed dementia
- Neuropsychiatric Inventory Questionnaire (NPI-Q) at least 3 items out of 12 items are rated as "present."
- Use of cholinesterase inhibitors, antidepressants and or antipsychotics medications is allowed, if on stable dosage for at least 2 months.
- Use of memantine and/or serotonin reuptake inhibitors is also allowed, if on stable dose for at least 2 months.
- Have a committed caregiver who is able and willing to assist them with medications, provide study participant information, and attend all study visits.

- Sufficient English language skills to complete all testing.
- MMSE score of 25 or lower.

Exclusion

- MMSE > 25
- Participants who started using antipsychotics or anticholinergics within the previous 2 months.
- Participants on blood thinners such as warfarin (Coumadin, jantoven), rivaroxaban (xarelto), fondaparinux (arixtra), dibigatran (pradaxa), apixaban (eliquis) dalteparin (fragmin), enoxaparin (lovenox). Aspirin use is allowed.
- Participants without an identified caregiver.
- Participants with delirium caused by medicinal poisoning or drug intoxication.
- Participants who have had the following diseases before the onset of cognitive impairment:
 - 1. Alcoholism
 - 2. Manic depression or bipolar disorder
 - 3. Schizophrenia
- Participants with malignancy or an acute inflammatory disease.
- Participants with critical circulatory, respiratory, kidney, or liver disease or diabetes.
- BMI of >30.
- Participants who have taken Feru-guard, ferulic acid, or Angelica archangelica supplementation within the last year.
- Enrollment in another clinical trial or treatment study within the previous 6 months.

D.2.3. Screen failure

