The NPI-Q [46] is a structured interview with a caregiver or qualified study partner (defined as having direct contact > 2 days/week) that evaluates both presence and severity of 12 neuropsychiatric features which include: delusions, hallucinations, dysphoria, anxiety, agitation/aggression, euphoria, disinhibition, irritability, lability, apathy, aberrant motor behavior, night-time behavior, and appetite/ eating changes [47]. If the response to the domain question is "No", the informant goes to the next question. If "Yes", the informant then rates both the Severity of the symptoms present within the last month on a 3-point scale ranging from 1 to 3 (mild to severe). Change in overall NPI-Q score between baseline and at 12 weeks will be the primary outcome measure. A modification of the original NPI is the addition of a Caregiver Distress Scale for evaluating the psychological impact of neuropsychiatric symptoms reported to be present. For each feature the caregiver distress score ranges from 1-5 (No distress to extreme distress). The caregiver distress subscale score is the sum of the distress scores for each of the 12 features. Change in overall NPI-Q subscale of caregiver distress score which is the between baseline and at 12 weeks will be a secondary outcome measure.

Clinical Dementia Rating (CDR)

The CDR [48] measures dementia severity and is a global rating of dementia with scores ranging from 0 to 3 (0, 0.5, 1, 2, and 3) rated by a semi-structured participant and informant interview [49]. A trained rater synthesizes information of cognitive performance and functional abilities based on 6 domains which include memory, orientation, judgment and problem solving, community affairs, home and hobbies, and personal care. The scale has good inter-rater agreement [49].

Montreal Cognitive Assessment (MoCA)

A rapid screening instrument for assessing different cognitive domains [50]. Subjects are asked to do the following tasks: 1.) Join 10 randomly displayed numbers and letters in an alternating and sequential fashion. 2.) To measure visuoconstructional skills, accurately copy two drawings, a cube and a clock. 3.) Provide the names of three animals represented by drawings. 4.) Remember a list of 5 words. This is repeated 2 times. After a delay, subjects again recall as many words as possible. 5.) To measure

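### As worded, the NPI-Q caregiver distress sum carries one point for every symptom present, so a change in symptom count moves this exploratory secondary outcome even when distress is unchanged

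*Combined protocol and SAP*

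**What the plan says.** Section E.7.1 describes how the NPI-Q is given and scored. When the informant answers no to a symptom, "the informant goes to the next question". The distress scale is introduced as a means of "evaluating the psychological impact of neuropsychiatric symptoms reported to be present". Its item scoring is "For each feature the caregiver distress score ranges from 1-5 (No distress to extreme distress", and its total is defined by "The caregiver distress subscale score is the sum of the distress scores for each of the 12 features".

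The same section makes the 12-week change in this sum a secondary outcome. Secondary Aim 2 in Section A uses it to study the "effect of Feru-guard supplementation on caregiver burden (NPI-Q subscale of caregiver distress"), and Section G.1 repeats that use while calling the aim exploratory. Section G.2 applies the same mixed model as for the primary outcome and mentions no adjustment for the number of symptoms.

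Section D.2.2 requires at least 3 of the 12 symptoms to be present at entry. The documents give neither a score for a skipped feature nor a total range for the distress subscale.

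**The concern.** Two caregivers who are equally undistressed can receive different scores. One whose relative has no symptoms gets nothing for each skipped item; one whose relative has several harmless symptoms gets 1 for each. The subscale then mixes how distressed the caregiver is with how many symptoms there are.

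This matters because the supplement is expected to reduce symptoms. If it does, the distress sum falls through the count alone, and part of an apparent caregiver benefit would restate the symptom result. The distortion can also run the other way and hide a real easing of distress when new, harmless symptoms appear. Since the pilot is meant to inform a larger trial, the mean and spread of this score may be carried forward.

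**Working it through.** **Inputs**, all from Section E.7.1 except the last:

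- Item range for a present symptom: 1 (no distress) to 5 (extreme distress), which is five levels.
- Absent symptom: question skipped, no rating taken.
- Subscale: sum over 12 features.
- Entry minimum: 3 symptoms present (Section D.2.2).

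The plan states no figure for this subscale, so there is none to reproduce.

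**Step 1: decompose the score.** Let k be the number of symptoms present and d the rating of each. If skipped items add nothing,

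S = sum of d = k + sum of (d - 1).

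The second term is distress above the lowest level. The first is a pure symptom count. The possible range is 0 to 12 × 5 = 60.

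**Step 2: decompose the change.** Change in S = change in k + change in sum of (d - 1). The between-arm difference in mean change splits in the same way, so the artefact in the treatment contrast equals the between-arm difference in the mean change of k. If that is zero, the contrast carries no artefact.

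**Step 3: compare codings.** A is the text as most naturally read (1-5, absent adds nothing). B scores absent as 1 (range 12 × 1 = 12 to 60). C subtracts 1 from each rating and scores absent as 0 (range 0 to 12 × 4 = 48).

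| Baseline to week 12 | A | B | C |
|---|---|---|---|
| 6 symptoms to 3, all non-distressing | 6 to 3 (-3) | 12 to 12 (0) | 0 to 0 (0) |
| 3 symptoms to 0, all non-distressing | 3 to 0 (-3) | 12 to 12 (0) | 0 to 0 (0) |
| 12 symptoms to 0, all non-distressing | 12 to 0 (-12) | 12 to 12 (0) | 0 to 0 (0) |
| 6 symptoms rated 3; three ease to 2 | 18 to 15 (-3) | 24 to 21 (-3) | 12 to 9 (-3) |
| 3 symptoms rated 2 ease to 1; 3 new non-distressing ones appear | 6 to 6 (0) | 15 to 12 (-3) | 3 to 0 (-3) |

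Under A, the first and fourth rows give the same -3, although distress is unchanged in one and falls by three steps in the other. The fifth row shows a three-step fall in distress scored as no change. Codings B and C remove both errors, because each gives absent and no distress the same value.

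**Step 4: the primary score.** NPI-Q severity runs from 1 (mild) to 3 (severe). Its lowest level already denotes a symptom of some severity, so the same flaw does not arise there.

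**The case against.** The strongest reply is that the value of a skipped item is inferred. The text says that each feature scores 1-5 and that all 12 are summed. Taken literally, an absent symptom could sit at 1, the total would run 12-60, and the artefact would vanish. That reading is possible, but it is stated nowhere and fits poorly with a skipped question and a scale confined to symptoms that are present. Even if it was intended, the skipped-item value and the range are missing, and two programmers could score the same forms differently.

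Several limits on importance do stand:

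- Aim 2 is exploratory, and the ZBI screening version and the caregiver SF-12 are collected alongside, neither scored this way.
- The scale concerns the impact of symptoms, so some dependence on symptoms is built in. Under coding C, a symptom rated 3 that resolves still lowers the sum by 2.
- No standard deviation for this subscale is given, so the practical weight of one point cannot be judged.
- The case report form is not among the documents, and the wording may be a drafting slip.

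A reader might infer that the entry rule biases the result, because a caregiver with no distress still starts at 3 or more. It does not: a constant offset cancels in change from baseline, and only a change in count matters. A reader might also infer a false-positive risk when the supplement does nothing. With no effect on symptoms or distress, randomization makes the count term equal between arms in expectation.

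**Conclusion.** The point holds in limited form. On the most natural reading of Section E.7.1, the distress sum contains one point per symptom present, and each change of one symptom moves it by 1 point with distress unchanged. The theoretical ceiling is 12 points, reached only if all 12 symptoms are present and then all disappear. The treatment contrast is distorted only to the extent that symptom counts change differently between arms. The within-arm changes that Section G.2 also promises would carry any change in count common to both arms.

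It would go too far to say that any distress benefit would merely repeat the NPI-Q result, or that the subscale was promised as a measure independent of symptoms. The documents define it through symptoms, and the term for distress above the lowest level is real information.

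The conclusion assumes that skipped items add nothing and that the form follows the protocol's 1-5 anchors. It concerns an exploratory secondary outcome and leaves the primary analysis as it is.

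**What to change.** In Section E.7.1 and the scoring program, give an absent symptom and a present, non-distressing symptom the same value, and state the total range. One way is to subtract 1 from each rated item and score absent as 0, so that the five levels become 0-4 and the total 0-48. This needs no new data and can be applied to forms already completed.

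Before programming, check the anchors on the case report form. If they differ from 1-5, correct the protocol and apply the same principle to the form's levels. A 0-5 item with a total of 0-60 should not be adopted on the protocol's text alone, because it would need a sixth level that the text does not describe.

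The cost is a sentence or two in the protocol, a line of code and a look at the form.
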